# PRÉCIS

## **Background:**

- Chronic graft-versus-host disease (cGvHD) is the leading cause of non-relapse morbidity and mortality in persons after allogeneic hematopoietic cell transplants.
- About 50% of persons with cGvHD have disease refractory to systemic corticosteroids and there is no standard second-line therapy.
- Thalidomide, a drug with immune-modulating effects, was active in advanced cGvHD but was difficult to use at appropriate doses.
- Pomalidomide is related to thalidomide but with higher potency and more favorable toxicity profile. It is active in multiple myeloma and myeloproliferative neoplasm-associated myelofibrosis. Preliminary data in humans with cGvHD are encouraging but data are limited.

## **Objective:**

• Primary: Determine whether pomalidomide is effective in persons with moderate or severe cGvHD not controlled by corticosteroids.

# **Eligibility:**

- Inclusion Criteria
  - Moderate or severe cGvHD per NIH criteria
  - Age 18 to 75 years old
  - Karnofsky performance score  $\geq 60\%$
  - Has cGvHD that did not respond to high-dose corticosteroids (average 0.5 mg/kg/d prednisone for  $\geq$ 8 weeks) or second-line therapy
  - Receiving stable or tapering doses of systemic therapy in the preceding 4 weeks
  - Agree to adhere to methods of contraception and other fertility control measures as prescribed by the protocol
- Exclusion Criteria
  - Acute GvHD (classic and late per NIH criteria)
  - Absolute neutrophils <1.0x10^9/L, platelets <75x10^9/L, estimated creatinine clearance <50 mL/min/1.73m^2
  - NIH lung score 3
  - Pregnant or lactating
  - Uncontrolled infection

# Design:

Randomized phase 2 trial with the single stage selection design. Patients will receive either a constant low dose of pomalidomide (0.5 mg/day) for six months or a strategy of increasing dose of pomalidomide from 0.5 mg/d up through each individual patients' maximum tolerated dose, with escalations by 0.5 mg/d every 2 weeks to a maximum of 2.0 mg/d. As an early stopping rule for futility, if after 7 patients have enrolled on either arm, 0 have responded, then no further patients will be accrued to that arm as soon as this can be determined. To protect patient safety, an early stopping rule will be implemented. With two arms, each of which has a maximal accrual of 16 patients, up to 32 evaluable patients will be randomized. Response assessments will occur

**Abbreviated Title:** Pomalidomide for cGvHD **Version Date:** 4/29/2025

every 3 months with primary efficacy endpoint evaluated at 6 months. Patients with responding disease will continue therapy for another 6 months.

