3.6.1 Criteria for removal from protocol therapy

- Completion of 6- or 12-month course of protocol therapy (depending on the level of response)
- Progressive cGvHD or malignancy requiring new line of systemic therapy
- Participant requests to be withdrawn from active therapy
- Unacceptable toxicity as defined in Section **3.3**
- Dose interruption longer than 35 days
- Positive pregnancy test
- Investigator discretion

The PI is to be notified of all discontinuations from study drug. The reason for dose modification/discontinuation should be recorded in the CRF and in the patient's medical records.

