**Eyes:** The primary measurement of lacrimal gland function in cGvHD is using the Schirmer's test. The test should be performed without anesthesia for both eyes (OU) unless physically inapplicable. The measurement of each eye and the average of measurements will be recorded in the CRF.

Mouth: Mouth assessments include:

(1) mucosal erythema by 0-3 grading based on the color intensity, (2) lichen-type hyperkeratosis by 0-3 grading based on the percentage of oral surface area, (3 ulceration by 0-6 based on percentage of oral surface area, and (4) mucoceles by 0-3 grading based on its total number of presence.

Hematopoietic: The measurements of hematopoietic response include:

(1) platelet count,

(2) eosinophil count and percentage.

White blood cell (WBC) count will be recorded on the Assessment Form but will not be used for response assessment.

**Gastrointestinal tract:** Gastrointestinal (GI) symptoms are graded through interview by the investigator according to 0-3 severity scales.

**Liver:** Involvement of liver is graded according to the levels of bilirubin and liver enzymes (AST and ALT).

**Lung:** The forced expiratory volume in the first second (FEV1) and single breath diffusion lung capacity for carbon monoxide (DLCO) is included as components for the lung function score (LFS). LFS is computed by the extent of FEV1 and DLCO compromise (>80% = 1, 70 - 79% = 2, 60 - 69% = 3, 50 - 59% = 4, 40 - 49% = 5, <40% = 6). Scores for FEV1 and DLCO are added and the sum reduced to an overall category according to following table (Table 5). Absolute values of both FEV1 and DLCO should be recorded in the CRF.

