#### 7.4.1 Principal Investigator/Research Team

The clinical research team will meet on a regular weekly basis when participants are being actively treated on the trial to discuss each participant. Decisions about dose level enrollment and dose escalation if applicable will be made based on the toxicity data from prior participants.

All data will be collected in a timely manner and reviewed by the principal investigator or a lead associate investigator. Events meeting requirements for expedited reporting as described in section 7.2.1 will be submitted within the appropriate timelines.

The principal investigator will review adverse event and response data on each participant to ensure safety and data accuracy. The principal investigator will personally conduct or supervise the investigation and provide appropriate delegation of responsibilities to other members of the research staff.

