# **10 STATISTICAL CONSIDERATIONS**

It is known from prior trials that the pomalidomide MTD is about 3 mg/d in persons with bone marrow disorders receiving therapies for cancer. Due to high frequency of pomalidomide dose de-escalation observed in preliminary cGvHD experiences when given at 3 mg/d, this study will explore clinical toxicity of gradual escalation doses below 3.0 mg.

The primary objective of this study is to determine if patients with cGVHD will experience an acceptable level of clinical response when treated with either a constant low dose of pomalidomide (0.5 mg/day) for six months or a strategy of increasing dose of pomalidomide from 0.5 mg/d up through each individual patients' maximum tolerated dose, with escalations by

0.5 mg/d every 2 weeks to a maximum of 2.0 mg/d. The study will thus randomize patients between fixed low dose and escalating dose to tolerance, and will be considered a randomized phase II trial with a selection design component.

In each of the two arms, the trial will be conducted using a single stage design. With 16 patients on each arm, an exact binomial test would have 90% power to detect a difference between a 5% response rate and a 30% response rate using a 0.10 one-sided significance level and an exact binomial test. In addition, after the trial has ended, the 80% and 95% confidence limits will be determined for each arm about the observed response proportion in order to aid in interpretation of the results. If there are 3 or more responses in 16 patients, this would be sufficient to rule out a 5% response rate and demonstrate consistency with 30% or better response rates.

At the conclusion of the study, if both arms are able to accrue to the full 16 patients, the arm with the greater number of responses will be selected for further investigation subsequently. That is, if the fixed, low-dose arm, or the increasing dose level arm, has the greater number of responses, then that arm would be studied further. In the event of a tie, the lower dose arm would likely be preferred. As an example, if the true probabilities of response on the two arms were 0.10 and 0.30, then the probability of correctly selecting the superior arm would be 93%, and if the true probabilities on the two arms were 0.15 and 0.30, the probability of correct selection would be 84%.

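### One clinician-scored 6-month response status is both the primary endpoint and the condition for continuing drug, with no described separation between the two uses; about 2.2% upgrading of non-responders would take the 5% test past its stated 0.10.

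*Combined protocol and SAP*

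**What the plan says.** Section 6.2.2 makes overall response at 6 months the primary evaluation point. The Précis has response assessed "every 3 months with primary efficacy endpoint evaluated at 6 months. Patients with responding disease will continue therapy for another 6 months". Section 3.1 says the same, and Section 3.6.1 lists as a reason for ending protocol therapy "Completion of 6- or 12-month course of protocol therapy (depending on the level of response").

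Response is recorded on the clinician form (Appendix G) at each 3-month visit. Skin involvement is an estimated body surface area and mouth findings are graded. GI "symptoms are graded through interview by the investigator according to 0-3 severity scales" (Section 6.2.2.1). Under Sections 3.1 and 6.2.2.1, stable disease counts as response for a patient who was progressive at entry, and Section 3.1 rests that call on the clinician's estimate of the preceding 3 months.

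Section 7.4.1 adds: "The principal investigator will review adverse event and response data on each participant". The same section has the team meet weekly on each participant and take decisions on dose escalation. No masked assessor or independent response review is described.

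The test is in Section 10: "With 16 patients on each arm, an exact binomial test would have 90% power". The null rate is 5%, the target is 30%, and the test is one-sided at 0.10. The decision rule is: "If there are 3 or more responses in 16 patients, this would be sufficient to rule out a 5% response rate". The arm with more responses is selected, and the lower dose arm is likely to be preferred in a tie.

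**The concern.** An investigator who believes a patient is benefiting can keep that patient on protocol drug past month 6 only if the patient is classed as a responder. Section 3.1 mentions compassionate access only beyond 12 months. That is an incentive to resolve borderline scores upward, and the same scores feed the primary test.

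Two things are at stake, with different causes:

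- **The test against 5%.** Every patient receives pomalidomide, so the continuation incentive exists in both arms, whether or not the assessor knows the dose. With a bar of 3 in 16, very few relabelled patients matter.
- **The choice between arms.** Here knowledge of the arm is what matters. If more is expected of one arm, its borderline cases may be read more generously.

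**Working it through.** **Inputs.** From Section 10: 16 patients per arm, null rate 5%, target rate 30%, one-sided 0.10, success at 3 or more, more responses wins, low dose preferred in a tie. Assumed, not in the documents: the share *u* of true non-responders scored as responders, shown from 0 to 10%.

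**1. The plan's own figures.** With X ~ Bin(16, p):

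- P(X ≥ 3 | p = 0.30) = 0.9006, against 90% stated.
- P(X ≥ 3 | p = 0.05) = 0.0429, inside 0.10.
- P(X ≥ 2 | p = 0.05) = 0.189, so 3 is the smallest valid cut-off.

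The design reproduces.

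**2. Effect of upgrading on the 5% test.** Apparent rate p = 0.05 + 0.95u.

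| u | apparent p | P(X ≥ 3) |
|---|---|---|
| 0 | 0.0500 | 4.3% |
| 1% | 0.0595 | 6.6% |
| 2% | 0.0690 | 9.4% |
| 5% | 0.0975 | 20.0% |
| 10% | 0.1450 | 41.6% |

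Solving P(X ≥ 3) = 0.10 gives p = 0.0710, so u = (0.0710 − 0.05)/0.95 ≈ 2.2%. That is 16 × 0.0210 ≈ 0.34 upgraded patients per arm on average. If exactly one non-responder in the arm is upgraded, the arm passes when the true count is at least 2, with probability 18.9%. Applying the futility stop at 0 of 7 changes little: 3.7% instead of 4.3% at u = 0, and 17.6% instead of 20.0% at u = 5%.

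**3. Effect on the selection, ties to low dose.** One upgrade in the escalating arm changes the choice only if the true counts tie. One upgrade in the low-dose arm changes it only if the escalating arm leads by exactly one.

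| low dose / escalating | upgrade in | P(choice changes) |
|---|---|---|
| 30% / 30% | escalating | 15.3% |
| 30% / 15% | escalating | 10.1% |
| 15% / 30% | low dose | 14.3% |

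**4. How much discretion the criteria leave.** Appendix H sets numeric bars. Skin starting at 25–50% of body surface must fall by 25 points, and below 25% no partial response is possible. Mouth at 4–7 must fall by 4. Schirmer, platelet, eosinophil and liver criteria are instrument or laboratory values. A GI change from 3 to 2, or from 2 to 1, does count as partial response, and that score comes from interview. Section 6.2.2.2 also lists clinician scales, range of motion and NIH organ scores as primary response measures, but Appendix H has no calculation for them. It is therefore unclear whether they can move the overall status.

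**5. Timing of the entry call.** Section 3.1 places the stable-or-progressive judgement at screening and before randomization. The study calendar in Section 3.5 marks it at baseline and marks randomization at screening. Read literally, the calendar lets the call be made with the arm already known.

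**The case against.** The strongest reply is that response here is calculated rather than declared. Partial response needs improvement in one organ and no progression in any other, and a mixed response counts as progression. Section 3.5 already schedules a response calculation, with body photography at baseline and 6 months. Under Section 9, monitors unaffiliated with the trial verify response assessment against source. All of this stands and narrows the room for upgrading. None of it is independent re-scoring of skin, mouth, GI or the entry call.

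It is also fair that no misclassification rate is documented, and that at 1% or 2% upgrading the test stays inside the plan's own 0.10.

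Four stronger readings are tempting and not supported:

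- *That upgrading will occur and an inactive drug will pass.* The documents show an incentive and an opening, not a rate. Even with perfect scoring, a 5% arm passes 4.3% of the time.
- *That one patient decides the selection in 44% of trials at 30%/30%, or 30% at 15%/30%.* Those are the chances that the counts lie within one of each other. They ignore the tie rule, and at 30%/30% neither choice is wrong.
- *That the plan declares open-label scoring.* It does not. Knowledge of arm is inferred from the absence of masking, the team's role in dosing (Sections 3.3 and 7.4.1) and diaries that list capsule strengths (Appendix O).
- *That masking examiners to dose would protect the 5% test.* It would not, because the continuation incentive is the same in both arms.

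**Conclusion.** The concern holds as a structural weakness. It is not an arithmetic error, and Section 10 reproduces. One status serves as endpoint and continuation gate, several of its inputs are judgements, and nothing described keeps the two uses apart.

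The size depends wholly on the assumed upgrade rate. The false-positive risk per arm exceeds the stated 0.10 only above about 2.2%, but a single upgraded patient in an arm takes it to 18.9%. A single upgrade changes the selection in about 10% to 15% of trials in the three cases computed, if ties go to low dose. The plan says only that this is likely.

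The case for acting is that the margin is thin and the remedy cheap, not that bias has been shown.

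**What to change.** Amend Section 6.2.2:

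1. For the primary analysis, derive CR, PR, SD and PD by program from the recorded organ values, using Appendices H and I only. Record the investigator's continuation decision in a separate field that cannot change the endpoint.
2. Enter and lock the month-6 values before that decision is recorded.
3. Take baseline and month-6 skin area from the dermatology examiner already scheduled in Sections 2.6 and 3.5, who is not told arm or dose.
4. Record the stable-or-progressive call before randomization, and reconcile Section 3.1 with the calendar in Section 3.5. The program needs this call to decide whether stable disease counts.

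Items 1, 2 and 4 protect the 5% test. Item 3 mainly protects the selection.

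The cost is wording, one data field and a short program, with no added patients. Limits remain. Masking will be imperfect and GI scores stay interview-based. Mouth scores stay with the clinician unless a dental examiner is available at month 6: dental evaluation is listed at baseline (Section 2.6), but the calendar shows no month-6 dental visit. The rule on who continues drug is the sponsor's and is not altered here.

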## STATEMENT OF COMPLIANCE

The trial will be carried out in accordance with International Council for Harmonisation Good Clinical Practice (ICH GCP) and the following:

• United States (US) Code of Federal Regulations (CFR) applicable to clinical studies (45 CFR Part 46, 21 CFR Part 50, 21 CFR Part 56, 21 CFR Part 312, and/or 21 CFR Part 812)

National Institutes of Health (NIH)-funded investigators and clinical trial site staff who are responsible for the conduct, management, or oversight of NIH-funded clinical trials have completed Human Subjects Protection and ICH GCP Training.

The protocol, informed consent form(s), recruitment materials, and all participant materials will be submitted to the Institutional Review Board (IRB) for review and approval. Approval of both the protocol and the consent form must be obtained before any participant is enrolled. Any amendment to the protocol will require review and approval by the IRB before the changes are implemented to the study. In addition, all changes to the consent form will be IRB-approved; an IRB determination will be made regarding whether a new consent needs to be obtained from participants who provided consent, using a previously approved consent form.

## 1 INTRODUCTION

## **1.1 STUDY OBJECTIVES**

- 1.1.1 Primary Objective:
- 1.1.2 Determine whether pomalidomide is effective in persons with moderate or severe chronic graft-versus-host disease (cGvHD) not controlled by corticosteroids.
- 1.1.3 Secondary Objectives:
- 1.1.3.1 Determine whether pomalidomide is safe in persons with moderate or severe cGvHD not controlled by corticosteroids.
- 1.1.3.2 Determine the immune-modulatory effects of pomalidomide in persons with moderate or severe cGvHD.
- 1.1.3.3 Determine limited pharmacokinetics after oral administration of pomalidomide.

## **1.2 BACKGROUND AND RATIONALE**

#### 1.2.1 Chronic Graft-Versus-Host Disease

cGvHD is an important late complication of allogeneic hematopoietic cell transplantation. It is a leading cause of mortality in persons more than 2 years post transplant. Symptoms of cGvHD usually appear within 2 years post transplant. Incidences range from 6%-80% depending on recipient age, donor type (related or unrelated, HLA matched or mismatched), graft type (blood, bone marrow or umbilical cord), graft manipulation or donor lymphocyte infusions. Chronic GvHD is strongly associated with prior acute GvHD (aGvHD). Traditionally the cutoff point between aGvHD and cGvHD was day 100 post transplant. In 2005 an NIH consensus project proposed two main GVHD categories, each with two subcategories: (1) "classic" aGvHD occurring within 100 days post transplant and (2) "persistent, recurrent or late" aGvHD. The broad

category of cGvHD includes: (1) "classic" cGvHD (without features or characteristics of aGvHD) and (2) an "overlap syndrome" with concordant features of cGvHD and aGvHD. cGvHD is a multi-organ alloimmune and autoimmune disorder characterized by immune dysregulation, immunodeficiency, impaired organ function and decreased survival. It requires prolonged ongoing immunosuppression and inter-disciplinary management.

## 1.2.1.1 Pathophysiology

The pathophysiology of cGvHD is poorly understood. T- (both Th1 and Th2) and B-cells play a role in the pathogenesis of cGvHD, suggesting a general loss of tolerance, including abnormalities in the function of regulatory T-cells (Tregs). Natural Tregs (CD4+,CD25+,FoxP3+) maintain self-tolerance. Studies in mice indicate Tregs can suppress GvHD and that a deficiency of Tregs worsens GHD. There are conflicting data in humans concerning role of Tregs in the development of cGvHD. A recent study suggested *in vivo* administration of low-dose IL-2 as a potential Treg-mediated therapeutic approach for severe cGvHD.

Several studies suggested that aGvHD is associated with predominant Th1-type immune response and cGvHD with Th2-type immune response. Th1 cells produce interferon-  $\gamma$  (IFN- $\gamma$ ) that mediates cell immunity, and Th2 cells produce interleukin (IL)-4, IL-5 and IL-13, which mediate humoral immunity. Following T-cell dysregulation, there is consequently cytokine dysregulation. In persons with cGvHD, higher levels of tumor necrosis factor- $\alpha$ , IL- 6, transforming growth factor- $\beta$ , IL-1 $\beta$  and lower levels of INF- $\gamma$  and IL-10 are reported.

Autoimmunity and autoreactive T-cells have an important role in cGvHD. Some studies have shown that host thymus is not required for induction of cGvHD and that quiescent autoreactive T- and B-cells in transplants from non-autoimmune donors may be activated and expanded to cause cGvHD. In contrast, involvement of thymus-dependent pathways in cGvHD development begins with injury to the thymus from a chemotherapy-conditioning regimen or aGvHD, leading to loss of B-cells with their ability to produce antibodies and to present antigen, which may enhance development of cGvHD. Autoantibodies like anti-nuclear, anti-mitochondrial, anti-parietal, anti-smooth muscle and anti-parotid are present in persons with cGvHD. Also, persons with autoantibodies had more cGvHD-associated symptoms than persons without autoantibodies. Autoantibodies against platelet-derived growth factor receptor (PDGFR) may play a role in cGvHD. These PDGFR- $\alpha$  autoantibodies stimulate thyrosine phosphorylation in a cascade of events contributing inflammation and fibrosis.

The studies report elevated levels of BAFF (B-cell activating factor of the TNF family), which is produced by T-cells and granulocytes. BAFF supports differentiation and survival of normal B-cells in persons with cGvHD and autoimmune diseases. Fuji et al. showed that in early-onset cGvHD, there are elevated sBAFF, sIL-2R $\alpha$ , sCD13, and anti-dsDNA levels. In late-onset cGvHD, sBAFF, anti-dsDNA and ANA are higher, suggesting that the B-cell activation is predominant. These observations create rationale for treatments with anti-CD20 antibodies in cGvHD.All of these pathways are potential targets for cGvHD therapy. However, to date no laboratory parameter is considered a reliable biomarker for the diagnosis, measurement of severity, prognosis or therapeutic effect in cGvHD.

#### 1.2.1.2 Clinical Manifestations

The usually affected organs in cGvHD are the skin, eyes, mouth, gut, liver, lungs, joints and genitourinary tract. Examples of diagnostic skin manifestations are sclerotic features and

#### **Abbreviated Title:** Pomalidomide for cGvHD **Version Date:** 4/29/2025

poikiloderma, lichen-type and hyperkeratotic plaques in the mouth or bronchiolitis obliterans in lung biopsy. The clinical manifestations of the disease are reminiscent of the autoimmune diseases such as systemic sclerosis, systemic lupus erythematosus or Sjögren syndrome. According to the NIH consensus global scoring system, cGvHD is categorized as mild, moderate or severe. Systemic immune-suppressive therapy is usually indicated in persons with cGvHD involving 3 or more organs or with a severity score of 2 or higher in any organ. Systemic therapy is also to be considered in persons with thrombocytopenia (platelets <100x10^9/L) or progressive onset during prednisone treatment. cGvHD eventually leads to impaired functional performance, deteriorating quality of life, increased risk of infections and death.

